3. OBJECTIVES, ENDPOINTS, AND ESTIMANDS

3.1. Objectives and Endpoints for Part A of ARGX-113-2009 (Phase 2 Proof-of-Concept Part of Study)

Table 3: Part A Objectives and Endpoints

Endpoints
Proportion of participants who are in CR while receiving efgartigimod PH20 SC or placebo and have been off OCS therapy for ≥8 weeks at week 36
Cumulative dose of OCS from baseline to week 36
 Proportion of participants who achieve an IGA-BP score of 0 while receiving efgartigimod PH20 SC or placebo and have been off OCS therapy for ≥8 weeks at week 36 Proportion of participants who achieve an IGA-BP score of 0 or 1 while receiving efgartigimod PH20 SC or placebo and have been off OCS therapy for ≥8 weeks at week 36 Proportion of participants who achieve an IGA-BP score of 0 or 1 while receiving efgartigimod PH20 SC or placebo at any time through week 36 Changes from baseline in the BPDAI activity score Proportion of participants who are in CR while receiving efgartigimod PH20 SC or placebo and have been receiving minimal OCS therapy for ≥8 weeks at week 36. (Minimal OCS therapy is defined as ≤0.1 mg/kg/day of prednisone [or an equivalent dose of another OCS]) Time to achieve the following: CDA CR CR while on minimal OCS therapy for ≥8 weeks CR/PR while off OCS therapy for ≥8 weeks CR while off OCS therapy for ≥8 weeks

Table 3: Part A Objectives and Endpoints (Continued)

Objectives	Endpoints										
Secondary (continued)											
To characterize the overall efficacy of efgartigimod PH20 SC in the treatment of participants with BP (continued)	 Cumulative OCS dose for the participant at the time points when they exhibit the following: CDA CR CR while on minimal OCS therapy for ≥8 weeks CR/PR while off OCS therapy for ≥8 weeks CR while off OCS therapy for ≥8 weeks Relapse Proportion of participants who receive rescue therapy before week 36 										
To evaluate the efficacy of efgartigimod PH20 SC in preventing relapse of BP	Proportion of participants who achieve CDA while receiving efgartigimod PH20 SC or placebo and remain free of relapse through week 36										
To evaluate the effect of efgartigimod PH20 SC on pruritus in participants with BP	 Changes from baseline in the 24-hour average itch score from the Itch NRS Changes from baseline in the 24-hour worst itch score from the Itch NRS 										

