To characterize the efficacy of efgartigimod PH20 SC in the treatment of participants with BP	4. Proportion of participants who are in CR while receiving efgartigimod PH20 SC or placebo and have been receiving minimal OCS therapy for ≥8 weeks at week 36. (Minimal OCS therapy is defined as ≤0.1 mg/kg/day of prednisone [or an equivalent dose of another OCS].)						
5. To evaluate the effect of efgartigimod PH20 SC on pruritus in participants with BP	Changes from baseline in the 24-hour average itch score from the Itch NRS						
Other Secondary							
To further characterize the overall efficacy of efgartigimod PH20 SC in the treatment of participants with BP	 Proportion of participants who achieve an IGA-BP score of 0 or 1 while receiving efgartigimod PH20 SC or placebo and have been off OCS therapy for ≥8 weeks at week 36 Proportion of participants who achieve an IGA-BP score of 0 or 1 while receiving efgartigimod PH20 SC or placebo at any time through week 36 Changes from baseline in the BPDAI activity score Time to achieve the following: CDA CR CR while on minimal OCS therapy for ≥8 weeks CR while off OCS therapy for ≥8 weeks Relapse Cumulative OCS dose for the participant at the time points where they exhibit the following: CDA CR CR while on minimal OCS therapy for ≥8 weeks CDA CR CR while on minimal OCS therapy for ≥8 weeks CR while off OCS therapy for ≥8 weeks Relapse 						

Table 4: Part B Objectives and Endpoints (Continued)

Objectives	Endpoints
Other Secondary (continued)	
To further characterize the overall efficacy of efgartigimod PH20 SC in the treatment of participants with BP (continued)	 Changes from baseline in the 24-hour worst itch score from the Itch NRS Proportion of participants who receive rescue therapy before week 36
To assess the safety and tolerability of efgartigimod PH20 SC administered to participants with BP	Incidence and severity of TEAEs, AESIs, and SAEs Vital sign measurements, physical examinations, ECGs, and clinical laboratory safety evaluations
To assess glucocorticoid-associated morbidity and evaluate the impact of efgartigimod PH20 SC in reduction of glucocorticoid toxicity	 The Aggregate Improvement Score (AIS) from the GTI The Cumulative Worsening Score (CWS) from the GTI The GTI Specific List (GTI-SL)
To evaluate the effects of efgartigimod PH20 SC on the QoL of participants with BP	 EQ-5D-5L scores over time DLQI scores over time ABQoL scores over time

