6.8.1.3. Oral Prednisone Dose Adjustment Regimen (Based on BP Disease Assessment)

Participants will receive IMP with concurrent OCS therapy. The recommended OCS dosing regimen is described below and displayed in Table 7.

The investigator should not deviate from the concurrent oral prednisone dosing regimen, except in matters where the safety of the participant may be compromised. After taking appropriate action to ensure the safety of the participants, such concerns should be documented and communicated to the sponsor's medical monitor and designee within 24 hours of the event.

For OCS doses not listed in Table 7, minimum and maximum recommended doses are provided. For participants with body weights of <45 kg or ≥110 kg, the investigator should propose OCS doses and inform the medical monitor to ensure consistency within the study.

Note: For the following list, "oral prednisone" refers to prednisone or an alternate OCS of equivalent dose strength.

- All participants will begin the study by taking oral prednisone 0.5 mg/kg/day starting at baseline (week 0; day 1).
- If the participant has not achieved CDA within 1-3 weeks of treatment with oral prednisone 0.5 mg/kg/day, then the dosage may be increased to 0.75 mg/kg/day for up to an additional 3 weeks. This period may be extended by 1 additional week (based on clinical judgment) to achieve CDA with an oral prednisone dosage of either 0.75 mg/kg/day or 1 mg/kg/day.

- A participant will be considered as a treatment failure if they do not achieve CDA after receiving the IMP with the prednisone dosing regimen described above. In case of treatment failure, IMP will be permanently discontinued (Section 7.1.1). Under these circumstances, the participant will be considered a nonresponder (Section 9.3.2).
- When CDA is achieved, the oral prednisone dosing regimen is adjusted as follows:
 - After CDA has been sustained for ≥2 weeks, the dose tapering schedule begins with the next lower oral prednisone dosage as listed in Table 7. Each new dosage must be maintained for at least 2 weeks provided that no new lesions (transient or nontransient) appear. Duration of tapering steps from escalated doses (>0.5 mg/kg/day) may be shortened based on clinical judgment.

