9.3.3. Secondary Endpoints Analysis

9.3.3.1. Analysis of Secondary Efficacy Endpoints (Part B Only)

For part B, there are 5 proposed key secondary endpoints subject to alpha control:

- 1. Cumulative dose of OCS from baseline to week 36.
- 2. Proportion of participants who achieve an IGA-BP score of 0 while receiving efgartigimod PH20 SC or placebo and have been off OCS therapy for ≥8 weeks at week 36.
- 3. Proportion of participants who achieve CDA while receiving efgartigimed PH20 SC or placebo and remain free of relapse through week 36.
- 4. Proportion of participants who are in CR while receiving efgartigimed PH20 SC or placebo and have been receiving minimal OCS therapy for ≥8 weeks at week 36.
- 5. Changes from baseline in the 24-hour average itch score from the Itch NRS.

Details on how to deal with the main ICEs for the proposed key secondary endpoints will be provided in the SAP.

The first proposed key secondary endpoint—cumulative dose of OCS from baseline to week 36— will be analyzed in the form of a normalized cumulative OCS dose (NCOD), normalizing by weight and by number of days in study and will be denoted as NCOD.

For the NCOD endpoint, the analysis of covariance (ANCOVA) model will be used to compare both study arms. The model will include treatment and the stratification variables will be considered as factors. Other secondary efficacy endpoints will be analyzed in a similar fashion, as described below:

- Cumulative OCS dose at the time the participant exhibits CDA, CR, and CR while receiving efgartigimod PH20 SC or placebo and receiving minimal OCS therapy for >8 weeks
- CR/PR while receiving efgartigimod PH20 SC or placebo and off OCS therapy for >8 weeks
- Relapse

In addition to using the measure NCOD for analyzing the cumulative dose of OCS use over the study duration, the term "cumulative OCS use (mg)" will be used and analyzed using descriptive statistics.

The second, third, and fourth proposed key secondary endpoints will be analyzed using a CMH test as specified for the primary endpoint. Other secondary efficacy endpoints that are expressed as responder proportions will be analyzed similarly.

The fifth proposed key secondary endpoint—changes from baseline in the 24-hour average itch score from the Itch NRS—is measured over time and will be analyzed using a mixed-effect model for repeated measures, and the least squares mean difference will be estimated at the prespecified time point.

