3.5.2 Derivation rules

Normalized cumulative OCS dose (NCOD) will be calculated based on prednisone equivalent doses. Prednisone equivalent dose is calculated as [dose of ATC]*[equivalence factor prednisone]/[equivalence factor ATC]. Following [equivalence factors] are used:

ARGX-113-2009

Statistical Analysis Plan

Final and Interim Analysis

Final 4.0 of 04NOV2024

- Betamethasone [1.5]
- Cortisone [37.5]
- Deflazacort [15]
- Dexamethasone [1.5]
- Fluocortolone [10]
- Hydrocortisone [30]
- Hydrocortisone sodium phosphate [30]
- Methylprednisolone [8]
- Methylprednisolone acetate [8]
- Methylprednisolone sodium succinate [8]
- Paramethasone [4]
- Prednisolone [10]
- Prednisone [10]
- Prednisolone acetate [10]
- Prednisone acetate [10]
- Prednisolone sodium succinate [10]
- Prednylidene [12]
- Rimexolone [20]
- Triamcinolone [8]

[figure not shown]
Example: calculation of equivalent dosage of 12 mg methylprednisolone: 12*10/8= 15 mg prednisone.

Only systemic use of oral medication is included.

NCOD (mg/kg/day) is calculated for different periods as [the sum of (equivalent doses taking into account daily dose frequency)/(body weight in kg)]/(period duration in days) with body weight of visit closest before or at each intake of OCS medication. If for a given day of analysis period, no record exists in the CRF indicating OCS use that day, the dose will be assumed to be 0 mg. NCOD will be calculated with and without considering main intercurrent events (see efficacy section 4.1.3.1). Additionally, the cumulative OCS dose (COD, in mg) over these periods will be calculated.

The denominator of the NCOD should cover all days on IMP treatment in the study, starting at baseline. Following periods are considered (including start and end of the period):

- Over the whole 2009 on IMP treatment period
- From first IMP administration until CDA or end of on IMP treatment period (whichever comes first)
- From first IMP administration until CR or end of on IMP treatment period (whichever comes first)

- From first IMP administration until CR while on minimal OCS therapy for ≥8 weeks or end of on IMP treatment period (whichever comes first)
- From first IMP administration until CR/PR while off OCS therapy for ≥8 weeks or end of on IMP treatment period (whichever comes first)
- From first IMP administration until CR while off OCS therapy for ≥8
 weeks or end of on IMP treatment period (whichever comes first)

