11) Time from CRoff onset to Relapse, calculated only in participants with CRoff as the difference between the first date of relapse and the first date CRoff was achieved. Similar calculations and censoring rules are applied as for 'time from CDA to Relapse'.

Time from CR onset to Relapse will be analysed in a similar way as 'time to CRmin'.

- 12) NCOD as calculated for the different subperiods. NCOD from CDA/CR onset until relapse will only be analysed in participants with CDA/CR respectively. Same analysis will be performed as for the primary estimand of the key secondary parameter with ICEs handled according a 'while on treatment' strategy.
- COD will be calculated for the on IMP treatment period and the subperiods mentioned before. Only descriptive statistics will be presented.
- 13) Changes from baseline at week 36 in the 24-hour worst Itch NRS score will be analysed in the same way as for the 24-hour average itch score in the key secondary analysis.
- 14) Proportion of participants who received rescue therapy before week 36. A 'treatment policy' approach will be applied by ignoring main ICEs. Same CMH model as proposed for the primary endpoint.
- 15) ABQOL (17 items), EQ-5D-5L (5 dimensions) and DLQI (10 items) are assessed by the investigator at baseline, Week 12, Week 26 and at Week 36/ETD/ESD. Frequency tabulations will be provided for the percentages of participants within each outcome of QoL questionnaire items. Additionally cumulative percentages (starting with the best outcome result) will be calculated. A 'treatment policy' approach will be applied by ignoring main ICEs. For participants who received rescue therapy, only assessments prior to or on the start date of rescue therapy will be considered.
- 16) EQ-5D-5L VAS score and DLQI score are assessed by the investigator at baseline, Week 12, Week 26 and at Week 36/ETD/ESD. A total ABQOL score is calculated as the sum of all 17 items score 0 to 3 with higher score indicating worse condition. Missing items are imputed with the average score of the present items if at least half (9) of the items are present. The total score is rounded to the highest integer. A 'treatment policy' approach will be applied by ignoring main ICEs. For participants who received rescue therapy, only assessments prior to or on the start date of rescue therapy will be considered.

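### Cumulative steroid dose at CDA and at CR is tested as dose per day to the event, which can reverse direction for CR and is insensitive to time to CDA

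*SAP*

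**What the plan says.** Protocol Table 3 (Part A) lists the endpoint as "Cumulative OCS dose for the participant at the time points when they exhibit the following", and Table 4 (Part B) has the same wording in substance. The milestones include CDA, CR, CR on minimal OCS for at least 8 weeks (CRmin) and CR off OCS for at least 8 weeks (CRoff). Protocol 9.3.3.1 normalises the whole-period dose by weight and by days in study. It then says the dose-at-event endpoints, beginning with "Cumulative OCS dose at the time the participant exhibits CDA, CR, and CR while receiving efgartigimod PH20 SC or placebo", are to be analysed in a similar way.

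SAP 3.5.2 defines NCOD as "the sum of (equivalent doses taking into account daily dose frequency)/(body weight in kg)]/(period duration in days") and lists the windows, among them "From first IMP administration until CR or end of on IMP treatment period (whichever comes first"). The same section also says that the NCOD denominator is to span every day on IMP from baseline.

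SAP 4.1.4 item 12 takes "NCOD as calculated for the different subperiods" and gives it the key secondary analysis, which under SAP 4.1.3.2 is an ANCOVA with a least-squares mean difference, confidence interval and p-value. For the undivided dose: "COD will be calculated for the on IMP treatment period and the subperiods mentioned before. Only descriptive statistics will be presented".

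The taper rule is in Protocol 6.8.1.3: "After CDA has been sustained for ≥2 weeks, the dose tapering schedule begins with the next lower oral prednisone dosage".

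**The concern.** The protocol names an amount of steroid. The SAP tests a rate: that amount divided by the time taken to reach the event. The divisor is itself an outcome that treatment is meant to shorten.

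The dose path makes this matter. Everyone starts at 0.5 mg/kg/day, and the dose falls on a schedule triggered by CDA, not by CR. Someone who reaches CR soon has a window made up largely of full-dose days. Someone who reaches CR late has a window diluted by weeks of low dose. The late responder takes more steroid in total yet can have the lower rate.

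At stake is a reported mean difference and p-value on NCOD to CR that could favour the slower arm, next to a time-to-CR test and a COD table pointing the other way.

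**Working it through.** **Inputs from the documents**
- Protocol Table 7, 70 to <75 kg: 35 mg/day at the starting level, then 20, 12.5, 10, 5, 2.5 and 0 mg/day; 50 mg/day at the 0.75 level.
- Protocol 6.8.1.3: taper begins once CDA has lasted 2 weeks; each step lasts at least 2 weeks. I use 14 days for each.
- SAP 4.1.4 item 5: CR can be declared on more than 0.10 mg/kg/day, so it may fall early in the taper.
- Last IMP at week 35, which is day 35 × 7 + 1 = 246.

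**Assumed:** event days (the documents give none), weight 70 kg, no relapse.

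**The SAP's own figure.** The only worked number in SAP 3.5.2 is the dose equivalence 12 × 10/8 = 15 mg, which reproduces. No NCOD value is stated.

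**Formulas.** C = total mg / 70. NCOD = C / days in window.

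**To CDA, no escalation**
- CDA day 8: 8 × 35 = 280 mg; C = 4.0; NCOD = 4.0/8 = 0.50.
- CDA day 22: 22 × 35 = 770 mg; C = 11.0; NCOD = 11.0/22 = 0.50.

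Escalation does register. At nominal mg/kg steps, escalation after day 21 with CDA on day 28 gives (21 × 0.5 + 7 × 0.75)/28 = 0.563. CDA on day 42 gives (21 × 0.5 + 21 × 0.75)/42 = 0.625.

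**To CR**
- Fast (CDA day 8, CR day 29): 21 × 35 + 8 × 20 = 895 mg; C = 12.8; NCOD = 0.441.
- Slow (CDA day 22, CR day 85): 35 × 35 + 14 × 20 + 14 × 12.5 + 14 × 10 + 8 × 5 = 1860 mg; C = 26.6; NCOD = 0.313.

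Mixing only these two profiles, 70/30 against 30/70 fast/slow:
- C: (0.7 × 895 + 0.3 × 1860)/70 = 16.9 against (0.3 × 895 + 0.7 × 1860)/70 = 22.4 mg/kg.
- NCOD: 0.7 × 0.441 + 0.3 × 0.313 = 0.40 against 0.3 × 0.441 + 0.7 × 0.313 = 0.35.

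The arm with less steroid has the higher NCOD, and no participant without CR is needed.

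**Where the reversal stops**
- *Only CDA faster.* CR 40 days after CDA in both: CDA day 8/CR day 48 gives 735 + 280 + 13 × 12.5 = 1177.5 mg, C = 16.8, NCOD 0.350. CDA day 22/CR day 62 gives 1225 + 280 + 162.5 = 1667.5 mg, C = 23.8, NCOD 0.384. The order is as expected.
- *Participants without CR.* Unescalated and held at 5 mg to day 246: 1225 + 280 + 175 + 140 + 169 × 5 = 2665 mg, C = 38.1, NCOD 0.155. Treatment failure stopping IMP on day 42: 21 × 35 + 21 × 50 = 1785 mg, C = 25.5, NCOD 0.607. For assumed fast/slow/no-CR mixes of 60/20/20 against 20/40/40:

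| Participants without CR | NCOD, faster arm | NCOD, slower arm |
|---|---|---|
| All held at 5 mg | 0.358 | 0.275 |
| Half and half | 0.403 | 0.366 |
| All treatment failures | 0.448 | 0.456 |

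- *CRmin and CRoff, achievers on the minimum taper (nominal steps).* For CDA on day 7, 14, 21, CRoff gives 21.5/147 = 0.146, 25.0/154 = 0.162, 28.5/161 = 0.177. CRmin gives 21.5/119 = 0.181, 25.0/126 = 0.198, 28.5/133 = 0.214. The order is as expected.

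**Simulation** (60 per arm, 300 runs, lognormal event times, nominal steps, 70% of those without CDA by day 21 escalated, t-test in place of the ANCOVA):
- Median CDA 10 against 14 days, CDA-to-CR 30 against 60 days. NCOD to CR was 0.412 against 0.329, significant against the faster arm in 100% of runs, while C was 18.0 against 25.4 mg/kg. NCOD to CDA favoured the faster arm in 41% of runs, C to CDA in 93%.
- CDA 10 against 20 days, CDA-to-CR 30 against 60: NCOD to CR significant against the faster arm in 77%.
- CDA 10 against 20 days, CDA-to-CR 40 in both: NCOD to CR 0.372 against 0.427, no reversal.

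**The other denominator.** If all 246 on-IMP days were used, fast and slow become 12.8/246 = 0.052 and 26.6/246 = 0.108. The reversal disappears.

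**The case against.** The strongest defence has four parts.

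- **The SAP follows the protocol.** Protocol 9.3.3.1 normalises by days in study and asks for a similar analysis of the dose-at-event endpoints. That is true, so the protocol shares the problem. It does not make a per-day rate the cumulative dose named in Tables 3 and 4.
- **The denominator may be all on-IMP days.** One sentence in SAP 3.5.2 can be read so, and then nothing reverses. The explicit formula and the list of windows favour the other reading, but the text supports both, and they can give opposite signs.
- **Consequences are limited.** The endpoint is not alpha controlled, the sub-period tables carry no interim or topline flag, COD is tabulated for the same windows, and time to each milestone is tested separately. All of this stands and limits the severity. It does not justify a p-value that can point the wrong way.
- **Testing undivided dose has its own bias.** Windows also close at the end of IMP. Someone stopping IMP on day 14 scores 14 × 35/70 = 7.0 mg/kg, better than the fast responder's 12.8. This stands and shapes the fix.

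A reader might infer that NCOD to CDA carries no information, that NCOD to CR always favours the slower arm, or that all the milestone windows fail alike. The documents do not support these. Escalation raises NCOD to CDA in the right direction. Relapse and treatment failure (Protocol 6.8.1.3 and 6.8.3) bring higher doses or early closure of the window. CRmin and CRoff keep their order among achievers on the minimum taper.

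**Conclusion.** The concern holds in a limited form. The analysis tests dose per day to the event where the protocol names cumulative dose. For CR, the direction can reverse under plausible event times: 0.441 against 0.313 mg/kg/day while the cumulative doses are 12.8 against 26.6 mg/kg. Whether it does so in this trial depends on how far treatment shortens the interval from CDA to CR and on what happens to participants without CR; the assumed scenarios run from a clear reversal to none. For CDA, the measure ignores time to CDA among unescalated participants and responds only through escalation. All event times and mixes are assumptions.

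It would be wrong to infer that the trial's steroid-sparing claim is compromised. That claim rests on the whole-period NCOD key secondary, which is unaffected, as is the primary endpoint.

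**What to change.** - **SAP 4.1.4 item 12:** for the sub-periods ending at CDA and at CR, present NCOD descriptively, without a least-squares mean difference or p-value, beside COD and the time-to-event results.
- **If a test is wanted:** apply the ANCOVA to weight-normalised cumulative dose (mg/kg) to the event, and only with a stated rule for participants who stop IMP or finish without the event. Without that rule, early stoppers score as steroid-sparing.
- **SAP 3.5.2:** state whether sub-period NCOD is divided by the sub-period's own length or by all on-IMP days, and reconcile the two sentences.
- **Protocol 9.3.3.1:** align the statement that these endpoints are analysed in a similar way to NCOD, or record the departure in SAP 6.1.

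Cost: SAP wording, since dose, weight and dates are already derived. The downside is the loss of an exploratory p-value, or one extra rule if the test is kept.

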2.3.2 Handling partially or completely missing dates in calculations

Partially missing date of BP disease onset / diagnosis will be imputed as follows:

- Missing day of disease onset / diagnosis will be imputed with first day of the month
- Missing day and month of disease onset / diagnosis will be imputed with January 1st.

If the imputed date of diagnosis is before the date of disease onset, date of diagnosis will be imputed with date of disease onset.

If the imputed date of disease onset is after the date of diagnosis, date of disease onset will be imputed with date of diagnosis.

OCS administration start dates with partially missing data will be imputed as follows:

- Missing day will be imputed with first day of the month or start date of the first phase, whichever comes latest.
- Missing day and month will be imputed with 1JAN or start date of the first phase, whichever comes latest.
- Completely missing date will be imputed with start date of the first phase.

OCS administration end dates with partially missing data will be imputed as follows:

- Missing day will be imputed with the last day of the month, the date of trial termination, or the cut-off date, whichever comes first.
- Missing day and month will be imputed with 31DEC, the date of trial termination, or the cut-off date, whichever comes first.
- Completely missing end date will be considered as still ongoing at trial termination or the cut-off date.

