3.2.2 Derivation rules

The following parameters will be derived:

- Age at informed consent, categorized (18 <65, 65 <75, 75 <85, >=85)
- BMI at screening, categorized (Underweight: < 18.5 kg/m², Normal weight: 18.5 -< 25 kg/m², Overweight: 25 -< 30 kg/m², Obese: >= 30 kg/m²)
- Race, categorized (Asian, Black or African American, White, Other)
- BPDAI activity score at baseline, categorized: <20, 20-56, >56
- Anti-BP180 antibodies at baseline, categorized: positive (≥20 RU/mL), negative (<20 RU/mL)
- Anti-BP230 antibodies at baseline, categorized: positive (≥20 RU/mL), negative (<20 RU/mL)
- Both anti-BP180 and anti-BP230 antibodies positive: if both of the above are positive
- Time since BP disease diagnosis (months): (date of first IMP date of diagnosis)*12/365.25

Notes:

- Partially missing dates will be imputed as detailed in section 2.3.2.
- Result will be rounded as detailed in section 2.3.4.
- Geographical region: Asia (Japan, China), North America (US, Canada), EU region+UK (EU/EEA/EFTA/UK), Rest of world
- OCS dose (per body weight) at baseline: since day 1 can be considered as a transition day, OCS dose on day 2 will be used as baseline.

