- From CDA onset until Relapse or end of on IMP treatment period (whichever comes first) (Only defined on the subset of participants that achieve CDA during the on IMP treatment period)
- From CR onset until Relapse or end of on IMP treatment period (whichever comes first) (Only defined on the subset of participants that achieve CR during the on IMP treatment period)

Details on how to derive the time till CDA, CR, CRmin, CR/PRoff and CRoff are included in section 4.1.4.

Following rules will be applied to allocate OCS administrations to the correct period:

- Only the start and stop date information will be considered
- Records with (partially) missing dates will be imputed as detailed in section 2.3.2.
- If dates of administration records overlap, the reported doses will be added together.
- If an administration is reported as dose per administration with frequency, then the doses should be allocated to the correct dates, taking the start date and the frequency into account. Example:
 - O Dose: 40 mg
 - Frequency: every other day
 - o Start Stop date: 01JAN2022 03JAN2022

[figure not shown]
This will result in:

- o 40 mg be allocated to 01JAN2022
- o 0 mg allocated to 02JAN2022
- o 40 mg allocated to 03JAN2022

The following parameters will be derived for IMP administration:

- Number of administrations: sum of all administrations of study drug.
 Two administrations are expected on day 1 and day 8.
- Number of loading doses: i.e., daily doses of 2000 mg (2 administrations of 1000 mg).

The following parameters will be derived for IMP self-administration by participant and by caregiver:

- Number of participants/caregivers receiving the self-administration training.
 - Number of training visits received by participant/caregiver.
- Number of participants/caregivers who were adequately trained and capable to self-administer efgartigimod.
- Number of training visits before being considered capable to selfadminister.

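### OCS date imputation ignores the adjacent dose record and overlapping doses are summed, so a partial, missing or shared date between taper steps inflates that participant's NCOD

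*SAP*

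**What the plan says.** SAP 3.5.1 records a start date, an end date and a dose for each OCS administration. SAP 3.5.2 allocates these to days for NCOD and cumulative OCS dose (COD). It works at date level ("Only the start and stop date information will be considered"), sends incomplete dates to SAP 2.3.2, and then applies the overlap rule: "If dates of administration records overlap, the reported doses will be added together". A day with no record gets nothing: if "no record exists in the CRF indicating OCS use that day, the dose will be assumed to be 0 mg". The worked example in that section doses the stop date itself ("40 mg allocated to 03JAN2022"), so stop dates are inclusive.

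SAP 2.3.2 handles incomplete OCS dates as follows:

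- Start: "Missing day will be imputed with first day of the month or start date of the first phase, whichever comes latest". If the month is missing too, 1 January is used in the same way.
- End: "Missing day will be imputed with the last day of the month, the date of trial termination, or the cut-off date, whichever comes first". If the month is missing too, 31 December is used in the same way.
- End wholly missing: "Completely missing end date will be considered as still ongoing at trial termination or the cut-off date".

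The only limits are the start of the first phase, trial termination and the data cut-off. The adjacent OCS record is not one of them.

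SAP 3.2.2 recognises a changeover day, but only for the baseline dose: "since day 1 can be considered as a transition day, OCS dose on day 2 will be used as baseline". SAP 3.5.2 has no counterpart for NCOD, whose period begins on day 1.

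**The concern.** Two OCS records can relate in two ways. They may be concurrent, such as two tablet strengths making one daily dose, and then adding is correct. Or one may replace the other, as in the taper of protocol section 6.8.1.3 and Table 7, and then only one dose applies on any day. The SAP does not distinguish the two. Its imputation always widens a record and its overlap rule always adds, so a stretched or shared boundary between successive steps can only raise the total.

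NCOD over the on-IMP period is the first key secondary endpoint listed in the protocol and is alpha-controlled in Part B. SAP 4.1.3.2 compares it by ANCOVA on means, and SAP 2.3.5 rules out outlier detection. No rule in the analysis would therefore remove an inflated value. COD and the sub-period NCODs use the same allocation.

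**Working it through.** **Plan's own figures.** Day-by-day allocation with inclusive dates reproduces the example in SAP 3.5.2: 40 mg every other day over three dates gives 40 + 0 + 40 = 80 mg. The equivalence example also reproduces: 12 × 10 / 8 = 15 mg.

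**Inputs.**

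- Doses from protocol Table 7, 70 to <75 kg column: 35, 20, 12.5, 10, 5, 2.5, then 0 mg/day.
- Minimum step length of 2 weeks, protocol section 6.8.1.3.
- On-IMP period of 246 days (day 1 to the week 35 dose).
- Assumed: constant weight of 70 kg, one record per taper step, 28 days at 35 mg and 14 days at each later step.

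**True value.** 35 × 28 + 14 × (20 + 12.5 + 10 + 5 + 2.5) = 980 + 700 = 1680 mg. NCOD = 1680 / 70 / 246 = 0.0976 mg/kg/day.

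**Error from one boundary.** Relative excess = dose × extra days / 1680. Means are taken over 365 possible calendar start dates.

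| Situation | Extra days | Excess |
|---|---|---|
| Stop day missing, 35 mg step | mean about 14.8; maximum 30 | mean +30.8%; maximum 35 × 30 / 1680 = +62.5% |
| Stop day missing, 20 mg step | maximum 30 | mean +17.5%; maximum 20 × 30 / 1680 = +35.7% |
| Start day missing, 20 mg step | mean about 14.6; maximum 28 (cut at day 1) | mean +17.4%; maximum 20 × 28 / 1680 = +33.3% |
| Stop date wholly missing, 35 mg step | 246 − 28 = 218 | 35 × 218 = 7630 mg, +454% (9310 mg, 5.5 times) |

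**Shared dates.** If each record stops on the day the next starts, each old dose is counted for one extra day: 35 + 20 + 12.5 + 10 + 5 = 82.5 mg. The total is 1762.5 mg, NCOD 0.1024, which is +4.9% or +0.0048 mg/kg/day. A 20 mg pre-baseline record ending on day 1 would raise this to 102.5 / 1680 = +6.1%.

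**Complete, non-shared dates.** No overlap, excess 0%.

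**Sensitivity to the assumed taper.** With the first step at 21, 28 or 42 days and later steps at 14 or 28 days:

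- 35 mg stop day missing: mean +18.0% to +36.0%, maximum +36.6% to +73.2%.
- 20 mg start day missing: mean +10.3% to +18.7%, maximum +19.7% to +33.3%.
- All five boundaries shared: +2.9% to +5.7%.

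**Counter-check.** A daily 22.5 mg entered as 20 + 2.5 mg for 14 days is correctly 315 mg when summed. Keeping only the larger record would give 280 mg. A blanket ban on summing would therefore be wrong.

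**The case against.** The strongest case against is that the rules are a fallback that may rarely act. Intake is kept in a daily diary reviewed at on-site visits (protocol 6.8.1.2), and the investigator records the daily dose since the last visit (8.2.1.1). Data are checked for gaps and inconsistencies and queried (10.1.10). A 35 mg record without an end date beside a later 20 mg record is an obvious query, so the 5.5-times case should not survive to analysis. This stands, and that case is not a basis for judging size.

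The documents also do not show that the CRF holds one record per taper step, or that successive records share a date. The transition-day remark concerns day 1 and the baseline dose only. With 2.5, 5, 10 and 20 mg tablets supplied (protocol Table 5), many overlaps may be genuine. This stands too: same-day recording is an inference, and the remedy must not delete real concurrent doses.

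A reader might infer that NCOD is double-counted throughout the trial, or that the treatment comparison is biased because participants with more dose changes collect more error. The documents support neither. The error needs a partial, missing or shared boundary date, and the same rules apply to both blinded arms. A differential effect is conceivable if the arms differ in number of dose changes or in dose at the affected boundary, but it is not shown.

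These points limit the size. They do not make the rule right in the cases it is written for, since SAP 2.3.2 prespecifies OCS-specific handling of exactly these incomplete dates.

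**Conclusion.** The concern holds in conditional form. Where a boundary date between successive taper steps is partial, missing or shared, the SAP counts both doses and biases NCOD and COD upward for that participant. In the assumed taper, one incomplete day on an early step costs roughly 17% to 31% on average, and shared dates at every boundary about 5%. These figures rest on one assumed 70 kg taper with one record per step. The frequency of such dates is not given. No SD or effect size for NCOD is given either, so the effect on the test or its power cannot be computed. This is worth correcting before database lock because the rule is wrong where it applies and the correction is cheap.

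**What to change.** In SAP 2.3.2, impute a partial or missing OCS end date no later than the day before the next replacing dose record starts. Impute a partial or missing start date no earlier than the day after the replaced record ends. Both should stay within the known parts of the date. If both dates at one boundary are incomplete, state which is imputed first.

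In SAP 3.5.2, where one record stops on the day its replacement starts, count one dose for that day, the new one. Keep summation for records that are truly concurrent: several tablet strengths making up one daily dose, or records whose complete dates overlap by more than the shared boundary day. Check these against the diary-based daily dose.

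The cost is SAP wording and a change to the OCS exposure program before database lock. Some record review is also needed, because the documents describe no CRF flag separating concurrent from replacing records.
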